### ***3.4.4.2 PD Analyses***

All PD parameters (section 3.3.3.5) including the change from baseline will be presented descriptively for each treatment arm.

Additionally, the change of severity (normal/abnormal) status along time will also be summarized for each treatment arm.

- In addition to the Safety/FAS population, it will also be done with the PP population

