#### **3.3.2 Control**

To study the PD, the most appropriate comparator is placebo, and as the participants do not have a parathyroid hormone deficiency, there are no concerns associated with that.

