### 8.3 Data Analysis

AEs will be presented in listings and Treatment Emergent Adverse Events (TEAEs) will be summarized. Individual results of laboratory tests (hematology, chemistry, and urinalysis) will be listed and change from baseline will be summarized using shift tables. Individual results of vital signs will be listed and observed values and changes from baseline will be summarized.

Individual results of quantitative ECG parameters from the 12-lead safety ECGs will be listed and observed values and changes from baseline will be summarized and analyzed consistent with the ICH E14 (3).

All summaries will be performed by placebo and each EXT608 dose level. Placebo data will be pooled across cohorts. Physical exam findings will be presented in data listings.

Concentrations of EXT608 will be summarized by dose over each scheduled sampling time using descriptive statistics. Individual plasma concentration data versus time will be presented in a data listing. PK parameters will be summarized by dose using descriptive

statistics. Dose proportionality will be assessed graphically and using a power model. PD will be presented in listings and summarized by dose and time point.

Detection of ADA and NAbs will be presented in listings and summarized by dose and time point.

No formal hypothesis testing will be conducted as part of this study.

DMB data packages will be based on the FAS for safety and PP for PK/PD.

Further details are described in the Statistical Analysis Plan.

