### 1.2.2 Secondary Objectives

The secondary objectives are to assess:

- Single dose PK including AUC0-24h, AUC0-48h, AUC0-28d, AUC0-∞, Cmax, Tmax, T1/2, λz, Cl/F and Vz/F.
- Single dose PD by post-dose change from baseline in serum chemistries with particular attention to Se-Ca, phosphate, magnesium, and creatinine. Urinalysis will also be performed.

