**Figure 1 Study Design**

## EXTBIO EXT608-101 Statistical Analysis Plan, V2, 2023-JULY-04

### 2.1.2 Randomization

Treatment allocation is performed in the EDC in a manner that ensures only the unblinded pharmacist or unblinded monitoring person know the treatment code. The treatment assignment is computer generated by the EDC at the point of randomization.

- Participants are randomized 3:1 EXT608:Placebo in blocks of 4.
- A Pocock-Simon (Pocock and Simon 1975) allocation minimization procedure is implemented into the randomization process to ensure the balance between each treatment arm.
- The balance procedure is based on the serum calcium (mg/dL) obtained at visit Day -1 of each participant.
- Participants who discontinue prematurely may be replaced at the discretion of the Sponsor.

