### ***3.4.4.1 PK Analyses***

All PK parameters (section 3.3.3.2) will be presented descriptively for each treatment arm.

A simple ANOVA model with treatment arm as the factor will be applied to each PK parameter to compare the active treatment arms to the pooled placebo group. The estimated mean difference and 95% Confidence Interval between each treatment arm and the placebo group will be presented. The corresponding p-value will also be reported although we do not expect it to be significant given the small sample size.

Additionally, a statistical model will be attempted to model the dose response of each PK parameters. The mode will not be pre-defined. We will plot the mean of each PK parameter against the dose and find an appropriate model if any.

- In addition to the Safety/FAS population, it will also be done with the PP population

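### Placebo is justified as the comparator for PD, but the SAP plans no placebo-adjusted PD estimate or interval; its only placebo contrast is on PK parameters, where it cannot be run

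*SAP*

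**What the plan says.** On the role of placebo, Protocol 3.3.2 states: "To study the PD, the most appropriate comparator is placebo". PD is a secondary objective, worded in SAP 1.2.2 as "Single dose PD by post-dose change from baseline in serum chemistries with particular attention to Se-Ca, phosphate, magnesium, and creatinine". Protocol 1.2 adds that the data should help choose pharmacologically active doses for later studies.

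On the PD analysis, SAP 3.4.4.2 has two elements: "All PD parameters (section 3.3.3.5) including the change from baseline will be presented descriptively for each treatment arm", and "Additionally, the change of severity (normal/abnormal) status along time will also be summarized for each treatment arm". Both are done in the FAS and the PP population. Protocol 8.3 agrees: "PD will be presented in listings and summarized by dose and time point". It also pools placebo across cohorts, shows it alongside each dose level, and rules out formal hypothesis testing.

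On placebo contrasts, SAP 3.4.4.1 contains the only one: "A simple ANOVA model with treatment arm as the factor will be applied to each PK parameter". It compares each active arm with pooled placebo and gives mean differences, 95% CIs and p-values. SAP 3.3.3.4 restricts PK parameters to participants who receive EXT608.

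On baseline, SAP 2.1.2 describes a minimization step: "The balance procedure is based on the serum calcium (mg/dL) obtained at visit Day -1 of each participant". SAP 3.3.3.5.1 defines the PD baseline twice, once as Day -1 and once as Day 0 pre-dose with Day -1 as fallback.

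**The concern.** The stated reason for having placebo is to study PD, yet no planned output estimates a PD effect relative to placebo. An arm's mean change from baseline contains the drug effect plus whatever the calendar and the setting do to serum chemistry: confinement in the unit, standardized meals, and sampling across the day against a pre-dose value. Concurrent placebo participants share these influences. Their data remove them from the estimate only if a difference is taken, and the difference is interpretable only with its uncertainty.

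The SAP places its placebo contrast where one side of the comparison does not exist. PK parameters are missing by design in placebo participants, whereas the PD variables are summarized for them too.

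At stake is the reading of which doses moved serum calcium, phosphate, magnesium or creatinine, and by how much. The primary safety objective is not affected.

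**Working it through.** **Design inputs.** SAP 2.1.1: up to 6 cohorts of 4, 3 EXT608 and 1 placebo, about 24 evaluable. SAP 2.1.2: "Participants are randomized 3:1 EXT608:Placebo in blocks of 4". Protocol 8.3: placebo pooled.

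**The plan's own figure.** 6 × 4 = 24, of whom 6 × 3 = 18 are active (3 per dose) and 6 × 1 = 6 are placebo. The stated 24 reproduces. No alpha, power, effect size or SD is given, because the sample size is explicitly not inferential.

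**Assumptions.** Six distinct doses; 3 per dose versus 6 pooled placebo; common residual variance. The documents give no SD for any PD variable and no baseline-outcome correlation r, so results are in units of the SD of change, with r assumed at 0.3, 0.5 and 0.8.

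**Half-width of the 95% CI, dose minus placebo.** The standard-error factor is √(1/3 + 1/6) = 0.707.

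1. What a reader could build by hand from the two table columns, with variance from those 9 participants: df = 3 + 6 − 2 = 7, so t(0.975, 7) × 0.707 = 1.67 SD.
2. Linear model with all seven groups: df = 24 − 7 = 17, so t(0.975, 17) × 0.707 = 1.49 SD.
3. The same model with the variable's baseline as covariate: df = 16. With equal variances at baseline and follow-up and balanced baselines, the SD of change is σ√(2(1 − r)) and the adjusted residual SD is σ√(1 − r²). Their ratio is √((1 + r)/2). The half-width is t(0.975, 16) × 0.707 × √((1 + r)/2) = 1.50 × √((1 + r)/2).

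| Assumed r | √((1 + r)/2) | Half-width (SD of change) | Narrower than 1.67 by | Narrower than 1.49 by |
|---|---|---|---|---|
| 0.3 | 0.81 | 1.21 | 28% | 19% |
| 0.5 | 0.87 | 1.30 | 22% | 13% |
| 0.8 | 0.95 | 1.42 | 15% | 5% |

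**Chance baseline imbalance.** A 1 SD (σ) difference in baseline between a dose arm and pooled placebo shifts the unadjusted difference in change by (1 − r)σ: 0.7σ at r = 0.3, 0.5σ at r = 0.5, 0.2σ at r = 0.8. Minimization on Day -1 calcium, with one placebo participant per cohort, cannot guarantee that each dose arm matches the pooled placebo group. It also does not act directly on phosphate, magnesium or creatinine.

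**If fewer cohorts run.** With four distinct doses, placebo n = 4 and df = 16 − 5 = 11. The all-arm half-width becomes t(0.975, 11) × √(1/3 + 1/4) = 2.20 × 0.764 = 1.68 SD.

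**The case against.** The strongest defence is that the plan is deliberately descriptive and says so consistently. The protocol plans PD summaries, excludes formal testing and does not size the trial for inference. A reader might infer that the SAP departs from the protocol; it does not. The exclusion of testing does not exclude estimates with intervals, however, and the SAP itself plans such intervals for PK.

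A reader might also infer that placebo PD data go unused, or that no uncertainty at all can be recovered. Protocol 8.3 puts pooled placebo beside each dose, and SAP 3.4.1 supplies N, mean and SD, so an unadjusted difference and interval can be worked out by hand. What is absent is the planned estimate and the baseline adjustment.

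A further tempting reading is that baseline calcium is balanced in allocation and then disregarded. The documents do not support it: the outcome is change from baseline, so baseline enters the analysis. Only its use as a covariate is missing, and at high r that gains little.

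Nor should the benefit be measured by setting the interval for one arm's mean on its own variance, t(0.975, 2)/√3 = 2.48 SD, against 1.49. Those are different quantities with different variance estimates. On the same pooled variance a single arm mean has half-width t(0.975, 17)/√3 = 1.22 SD, so the placebo contrast is wider. Its benefit is to remove time and setting effects; the gain in precision comes from the pooled variance and the covariate.

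Three technical objections stand as limitations:

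- Common variance cannot be checked well with 3 per dose. Five steps of up to 3-fold could span 3⁵ = 243-fold in dose.
- Five of the six placebo participants for any dose come from other cohorts dosed at other times, so the contrast is only partly randomized.
- Several variables at many times give many intervals.

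Finally, the safety plan, the simulations cited for sample size and the list of planned tables are not in the documents, and may hold more PD output than the SAP text shows.

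**Conclusion.** The point holds as a weakness in the choice of analysis. The comparison for which placebo is justified is not estimated in the SAP, and the contrast that is planned sits on parameters that do not exist for placebo participants. Adding the model takes the half-width for dose versus placebo from 1.67 SD of change (two columns by hand) to 1.49 (all arms), and to between 1.21 and 1.42 with baseline adjustment at r from 0.3 to 0.8. These figures assume six distinct doses, 3 per dose, 6 placebo, a common variance and balanced baselines. Repeat cohorts at one dose, which Protocol 3.1.5 allows, or fewer cohorts would change them.

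The intervals remain wide in every case. The gain is a placebo-corrected estimate with stated uncertainty, not a reliable test of each dose. It is worth making because it uses data already collected.

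**What to change.** - First reconcile the two PD baselines in SAP 3.3.3.5.1, and use the single chosen value both for the change score and as the covariate. State how it relates to the Day -1 calcium used for minimization.
- Remove the placebo ANOVA from SAP 3.4.4.1, since PK parameters are not derived for placebo participants.
- In SAP 3.4.4.2, for serum calcium, and for phosphate, magnesium and creatinine as supportive variables, fit a linear model of change from baseline. Treatment is a factor with levels for each dose and pooled placebo, and that variable's own baseline is the covariate. Fit it at the scheduled times and for each participant's peak.
- Report placebo-adjusted mean differences with 95% CIs and no p-values, labelled as estimation without multiplicity control. This respects Protocol 8.3.
- Keep the descriptive tables. State the common-variance assumption and the mostly non-concurrent origin of the pooled placebo group as limitations.

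The cost is about one SAP paragraph and a repeated simple model for four variables in the final analysis. It needs no new data, visits or participants.

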## EXTBIO EXT608-101 Statistical Analysis Plan, V2, 2023-JULY-04

### **3.4.4.3 Urine PD Volume**

The Urine PD volume will be summarized descriptively for each treatment arm.

### **3.4.5 Safety Analyses**

All Safety analyses will be done for Safety/FAS population.

#### **3.4.5.1 Adverse Event**

All AE (including TEAE and non-TEAE) will be listed.

Unless there are less than or equal to 5 TEAE in the whole study period, TEAE will be summarized as followed:

All TEAE will be presented with the number and percentage of participants and events (counts only), by System organ class (SOC) and by Preferred Term (PT).

The same summary will also be presented for the following group:

- All TEAE that may have a relationship to the study medication (i.e., site categorize the relationship in EDC as either Related, Probable, Possible, or Unlikely)
- Intensity Categorization Groups: Mild, Moderate and Severe
- Serious TEAE (SAE)

An overview of the above summary with count and percentage of participants will also be provided.

Any non-TEAE will be provided as listing only.

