### **4.3.2 Withdrawal documentation**

In case of withdrawal, the end of study Case Report Form (CRF) must be filled out including the reasons for the withdrawal, and if possible, a full end of study visit should be completed, and as a minimum the Investigator must evaluate that the participant is clinically stable for release from the study.

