## 1.2 OBJECTIVES

### 1.2.1 Primary Objective

The primary objective is to characterize the safety and tolerability profile of escalating dose levels of EXT608 when administered to healthy adult participants as a single injection as assessed by:

- Incidence, nature, and severity of adverse events (AEs) and withdrawals due to treatment emergent AEs (TEAEs) [Time Frame: Day 0 up to Day 28]
- Frequency and severity of post-dose change from baseline in hematology, serum chemistries, urinalysis, electrocardiogram (ECG), vital signs, and physical examination (Exam) findings [Time Frame: Day 0 up to Day 28]
- Percentage of participants with injection or infusion site reactions [Time Frame: Day 0 to Day 7]

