#### 3.4.2 Disposition of Participants

Descriptive summaries of participants' disposition will be provided. It will show the count and percentage.

The following will be presented for all screened participants:

- Screen failed
- Enrolled (qualified)
- Randomized

The following will be presented for all randomized participants:

- Cohorts
- Fully completed
- Early terminated
- Safety/FAS Population
- PP Population
- Treatment Randomized
- Treatment Received

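### SAP 3.4.5.1 drops the TEAE summary when the study has 5 or fewer TEAEs, contrary to Protocol 8.3, and the SAP text describes no summary of withdrawals due to TEAEs

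*SAP*

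**What the plan says.** The first measure under the primary objective (SAP 1.2.1, matching Protocol 2.1) is "Incidence, nature, and severity of adverse events (AEs) and withdrawals due to treatment emergent AEs (TEAEs"), over Day 0 to Day 28.

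Protocol 8.3 Data Analysis sets the reporting rule: "AEs will be presented in listings and Treatment Emergent Adverse Events (TEAEs) will be summarized". It adds: "All summaries will be performed by placebo and each EXT608 dose level". Placebo is pooled across cohorts, and no minimum number of events is set.

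SAP 3.4.5.1 Adverse Event first promises a listing: "All AE (including TEAE and non-TEAE) will be listed". It then makes the tables conditional: "Unless there are less than or equal to 5 TEAE in the whole study period, TEAE will be summarized as followed". The tables under that condition are all TEAEs by system organ class (SOC) and preferred term (PT), with the same layout for TEAEs by relationship, by intensity and for serious TEAEs. The section ends: "An overview of the above summary with count and percentage of participants will also be provided".

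On withdrawals, SAP 3.4.2 Disposition of Participants has one relevant line, "Early terminated", with no breakdown by reason. The reason is collected. Protocol 4.3.2 says that in case of withdrawal "the end of study Case Report Form (CRF) must be filled out including the reasons for the withdrawal".

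SAP 1.4 declares no modifications from the protocol's statistical section. SAP 4 refers to an attached spreadsheet for the planned listings, tables and figures. That file is not part of the documents.

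**The concern.** There are two gaps, and each stands without the other.

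The first is the threshold. It counts events pooled over all arms, while the primary question is tolerability by dose. A pooled total says nothing about how events are spread. A handful of events concentrated at the highest dose is an informative pattern in a dose-escalation study, and it is one for which the SAP would require no incidence by dose and no display against pooled placebo. The SAP departs from the protocol here on a primary measure without declaring it.

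The second is the withdrawal component. The SAP names withdrawals due to TEAEs as part of its first primary measure, but its text describes no table that yields them. In the disposition table as described, a participant who leaves because of toxicity is counted in the same line as one who leaves for convenience. This gap does not depend on how many TEAEs occur.

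**Working it through.** **1. Planned numbers.** SAP 2.1.1 plans up to 6 cohorts of 4, each 3 EXT608 and 1 placebo.
- Total: 6 × 4 = 24, which reproduces the planned number of evaluable participants.
- Active: 6 × 3 = 18. Pooled placebo: 6 × 1 = 6.
- The plan allows up to about 30 enrolled. No dropout rate is given. 24 / (1 − 0.20) = 30, so 30 fits an assumed 20% non-evaluable.

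**2. The two rules side by side.**

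| TEAEs in the whole study | Protocol 8.3 | SAP 3.4.5.1 |
|---|---|---|
| 6 or more | Summary by placebo and each dose | SOC/PT tables and overview |
| 5 or fewer | Summary by placebo and each dose | Listing only |

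The overview does not fill the second row. It is an overview of the conditional summary, so on its natural reading it falls under the same condition. SAP 3.4.5.1 also does not say that TEAE tables are by arm, whereas SAP 3.4.5.2 to 3.4.5.5 do say so for laboratory results, vital signs, ECG and injection site reactions.

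**3. What can sit at or below the threshold.**
- Spread evenly, 5 events are 5/24 = 0.21 per participant (5/30 = 0.17 if 30 are enrolled).
- Concentrated in one dose group of 3, they are 5/3 = 1.67 per participant. All three could be affected: 3/3 (100%) against 0/6 on pooled placebo if all six cohorts run as planned. No table is then required. This is an extreme case, chosen to show what the rule permits.

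**4. How often the condition would apply.** The documents give no TEAE rate, so a range is assumed. With N participants and r TEAEs per participant, take X as Poisson with mean m = N × r. Then P(X ≤ 5) = Σ (k = 0 to 5) e^(−m) m^k / k!.

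| Assumed r | N = 24: m | P(X ≤ 5) | N = 30: m | P(X ≤ 5) |
|---|---|---|---|---|
| 0.1 | 2.4 | 0.96 | 3 | 0.92 |
| 0.2 | 4.8 | 0.65 | 6 | 0.45 |
| 0.3 | 7.2 | 0.28 | 9 | 0.12 |
| 0.5 | 12 | 0.02 | 15 | 0.003 |

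A binomial check with at most one event per participant gives 0.97, 0.66, 0.23 and 0.003 for N = 24, and 0.93, 0.43, 0.08 and 0.000 for N = 30. The answer depends almost wholly on the assumed rate.

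**5. Withdrawals due to TEAEs.** The TEAE groups in SAP 3.4.5.1 are relationship, intensity and seriousness. None is withdrawal. Disposition gives one undivided count. So no summary in the SAP text yields the component at any TEAE rate.

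The size of one case in a dose group made up of one cohort depends on replacement:
- Not replaced: 1/3 = 33%.
- Replaced: Protocol 3.3.4 and 4.4 give the replacement the same treatment assignment, and SAP 3.1.1 keeps the dosed, replaced participant in the FAS. The group is then 4, and the proportion is 1/4 = 25%.

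**The case against.** A reader might infer that adverse events could go unreported. The documents do not support that. The AE listing is unconditional, and with five or fewer events a colleague could build the table by hand. What stands against this is narrower: hand tabulation is not a pre-specified by-dose summary, and the protocol promised one.

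A reader might also infer that the condition is likely to apply. That cannot be shown. Protocol 6.4 records every positive injection site finding as an AE, and Protocol 6.3.1 and 6.7 do the same for new findings at the last physical exam and for clinically relevant ECG changes. Over 24 to 30 participants followed to Day 28, more than 5 TEAEs may well occur.

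Third, tolerability by dose does not rest on this table alone. Injection site reactions, vital signs, ECG and laboratory shifts are summarised by arm whatever the TEAE count, and the DMB reviews each cohort's data through Day 7. This is correct, so the gap should not be read as a failure of safety oversight. None of those displays gives AE incidence, however.

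Fourth, Protocol 8.3 leaves further detail to the SAP and plans no formal testing. Both are true. But a condition that cancels a summary contradicts the protocol rather than adding detail to it, and SAP 1.4 says nothing has changed.

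Last, a reader might conclude that the SAP definitely provides no count of TEAE withdrawals. The table list is in a file not available here, so that goes too far. The supportable statement is that the SAP text describes none.

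**Conclusion.** The point holds on the text, at moderate weight. SAP 3.4.5.1 replaces with a listing a summary that Protocol 8.3 requires without condition, on the first primary measure and undeclared in SAP 1.4. No summary described in the SAP text gives withdrawals due to TEAEs, which the SAP itself names in that measure.

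The loss is the pre-specified incidence by dose against pooled placebo. The underlying data are kept. At the extreme, a 3/3 against 0/6 pattern would require no table. The chance that the condition applies runs from about 0.96 to 0.003 across assumed rates of 0.1 to 0.5 TEAEs per participant and N of 24 to 30, so no single likelihood can be claimed. One TEAE-related withdrawal is 33% of a one-cohort dose group without replacement and 25% with it.

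The contradiction over the threshold rests on no assumption. The withdrawal gap is subject to the unseen table list.

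**What to change.** In SAP 3.4.5.1:
- Delete the condition on 5 or fewer TEAEs.
- State that the TEAE overview and the SOC/PT tables are always produced, by pooled placebo and each EXT608 dose level, with participants n (%), event counts and zeros shown.
- Add a row *TEAE leading to withdrawal*. Identify these events from the AE record (action taken and outcome, Protocol 6.10.1.1) and reconcile them with the reason on the end-of-study CRF. The CRF reason alone is not enough for SOC/PT tables, because MedDRA coding is applied to AE records. The protocol gives no response options for action taken, so the SAP should say which entries count.

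In SAP 3.4.2, split early terminations by reason, and check the attached table list against these changes.

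The cost is SAP wording and one or two extra table rows, using data already planned for collection. The downside is that some tables may be sparse if few events occur.

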## 6.10 Safety Variables and Safety Reporting

### 6.10.1 Adverse Events

#### 6.10.1.1 Adverse Events

An Adverse Event (AE) is defined as any untoward medical occurrence in a participant or clinical investigation participant administered a pharmaceutical product and which does not necessarily have to have a causal relationship with this treatment. An AE can therefore be any unfavorable and unintended sign (including an abnormal laboratory finding, for example), symptom, or disease temporally associated with the use of a medicinal product, whether or not it is considered related to the medicinal product.

Adverse events will be collected from the time informed consent is signed and until the Follow-Up or Early Termination visit.

All participants will be queried, using non-leading questions, about the occurrence of AEs at each study visit. When possible, a constellation of signs and/or symptoms should be identified as one overall event or diagnosis. All AEs for randomized subjects will be recorded in the eCRF and the subject's source documents. Adverse events for subjects who are screened but not subsequently randomized in the study will be recorded only in the subject's source documents. The following data should be documented for each AE:

- Description of the events
- Classification of “serious” or “not serious”
- Date of first occurrence and date of resolution (if applicable)
- Severity
- Causal relationship to study drug
- Action taken
- Outcome
- Concomitant medication or other treatment given

Adverse events will be rated a mild, moderate or severe intensity using the following definitions:

- Mild: “Mild” events are usually transient and do not interfere with the participant’s daily activities.
- Moderate: “Moderate” events introduce a low level of inconvenience or concern to the participant and may interfere with daily activities.
- Severe: “Severe” events interrupt the participant’s usual daily activities.

The causality will be rated in the following categories:

- Unlikely: An “unlikely” relationship suggests that only a remote connection exists between the investigational study product and the reported AE. Other conditions, including chronic illness, progression or expression of the disease state or reaction to concomitant medication, appear to explain the reported AE.

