- Possible: A “possible” relationship suggests that the association of the AE with the investigational study product is unknown; however, the AE is not reasonably supported by other conditions.
- Probable: A “probable” relationship suggests that a reasonable temporal association of the AE with study product functionality exists and, in the Investigator’s clinical judgment, it is likely that a causal relationship exists between the study product’s functionality and the AE, and other conditions (concurrent illness, progression or expression of disease state or concomitant medication reactions) do not appear to explain the AE.

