### 3.3.4 Safety Variables

#### 3.3.4.1 *Adverse Events (AE)*

All observed or volunteered adverse events regardless in the treatment group or suspected causal relationship to the investigational device are captured in the EDC.

For all AEs, reformatting maybe applied and necessary transformation/Substitution may be needed as specified below:

- If an AE has known onset date but unknown onset time, then 12:00 will be used to substitute the onset time
  - The purpose of this substitution is for the determination of the TEAE
- If an AE has unknown onset date, no substitution will be done.

Treatment-emergent adverse event (TEAE) is defined as a post-baseline adverse event with onset date and time after the initiation of study treatment.

- Baseline is the IP administration date and time
- In this study, TEAE are the AEs that occur after the first successful IP administration.
  - If the AE has an unknown onset date, it will be assumed to be non-TEAE unless the investigational site confirms it is an TEAE

AE Coding:

- AE will be coded with latest available, at the time of coding, MedDRA code.

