## 4 List of planned listings, table and figures

Please see the attached Table of Contents Excel file.

Note that this is the planned Table of Contents, based on the actual data, table numbers, table names and structures may change.

EXTBIO EXT608-101 Statistical Analysis Plan, V2, 2023-JULY-04

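### The SAP's summary of possibly drug-related TEAEs includes events rated Unlikely, so on the protocol's causality scale it leaves nothing out and repeats the all-TEAE table

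*SAP*

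**What the plan says.** Protocol 6.10.1.1 has the investigator rate causality on three levels. Unlikely "suggests that only a remote connection exists between the investigational study product and the reported AE", and its definition adds: "Other conditions, including chronic illness, progression or expression of the disease state or reaction to concomitant medication, appear to explain the reported AE". Possible means the association is unknown; "however, the AE is not reasonably supported by other conditions". Probable means a causal link is judged likely. There is no level for not related, and none called Related.

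SAP 3.4.5.1 asks for all TEAEs by system organ class and preferred term. It then asks for the same layout for TEAEs with a potential link to study medication, meaning that the "site categorize the relationship in EDC as either Related, Probable, Possible, or Unlikely". Further tables cover intensity and serious TEAEs, and an overview brings the groups together. The summaries are planned "Unless there are less than or equal to 5 TEAE in the whole study period". SAP 1.4 declares no departures from the protocol's statistical section. The table shells are in a separate file that was not available, and SAP section 4 notes that "based on the actual data, table numbers, table names and structures may change".

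Two rules in SAP 3.3.4.1 decide which events count as TEAEs when onset is not fully known. For the date: "If the AE has an unknown onset date, it will be assumed to be non-TEAE unless the investigational site confirms it is an TEAE". For the time, when the date is known, "then 12:00 will be used to substitute the onset time".

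**The concern.** A table of possibly related events is useful because it separates events the investigator attributes, at least tentatively, to the drug from events thought to have another cause. If the group includes the lowest level of the scale, it makes no such separation. Adverse events are the first component of the primary objective, and the protocol's escalation rules turn on Grade 3 events suspected to be related to study drug, so attribution matters in this trial. Nothing in the documents makes this table an input to escalation. What is at stake is how the final report describes causality.

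The onset rules raise a smaller question. Non-TEAEs appear only in listings, so an event that in fact began after dosing but is classified as non-treatment-emergent drops out of every TEAE summary.

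**Working it through.** The documents give no figure on this point to reproduce. The main check compares two lists.

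**Causality group**

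- Protocol scale (6.10.1.1): {Unlikely, Possible, Probable}, 3 levels.
- SAP group (3.4.5.1): {Related, Probable, Possible, Unlikely}, 4 labels.
- Protocol levels inside the SAP group: 3 of 3. Protocol levels left out: 0 of 3.
- SAP labels not on the protocol scale: 1 of 4 (Related).

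Every TEAE rated on the protocol scale is therefore in the group, and the participant and event counts equal those for all TEAEs. Only a TEAE with missing causality would fall outside, and the SAP has no rule for that case.

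The result depends on what the EDC list holds, which the documents do not show:

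| Levels in the EDC (assumption) | Inside the SAP group | Same as the all-TEAE table? |
|---|---|---|
| The protocol's three | 3 of 3 | Yes |
| The SAP's four | 4 of 4 | Yes |
| The SAP's four plus Not related | 4 of 5 | Can differ |

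With Unlikely removed, the group holds 2 of 3 protocol levels and can differ from the all-TEAE table.

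Threshold: summaries are dropped at 5 or fewer TEAEs, so the point arises only with 6 or more.

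**Unknown onset date**

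AEs are collected from consent (protocol 6.10.1.1), and SAP Table 1 places screening from Day -28 to Day -2. Let s be the days from consent to dosing. For a completer seen at nominal Day 28, the post-dose share of the collection window is 28/(28 + s).

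- s = 28: 28/56 = 50.0%.
- s = 2: 28/30 = 93.3%.

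The non-TEAE default thus assigns an undated event to the equal or shorter part of the window. These are shares of calendar time, not probabilities of onset. The number of undated events is not given.

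**Unknown onset time on Day 0**

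With onset set to 12:00, a Day 0 event counts as a TEAE only if dosing was before 12:00. For anyone dosed after noon it becomes pre-dose. The documents give no clock time for dosing. The urine schedule in protocol 6.8.2.2 (morning void before dosing, a 4-hour collection, then one lasting to bedtime) suggests dosing earlier in the day but does not prove it.

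**The case against.** The strongest reply is that the SAP defines the group by what the site enters in the EDC, not by the protocol scale. Related is not a protocol level, which suggests the SAP was written from a different list, and naming the levels that belong to the group suggests at least one does not. With a Not related option, the table is a true subset. This stands as a condition on the duplication. It does not dispose of the point: the group would still pool Unlikely with Possible, whose definitions pull in opposite directions, and the EDC would then use a scale the protocol does not describe.

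Second, a remote connection is not no connection, so including Unlikely fits the group's label and is cautious for a first-in-human study. That may be the intention, but the SAP does not say so and describes no split by level. Whether the table shells plan one cannot be checked.

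Third, the impact is small. The analysis is descriptive, causality is recorded for every AE, and all AEs are listed, so a reader could probably separate Unlikely events by hand. That is right, and it is why the point is minor.

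On the onset rules, participants stay in the unit for at least 72 hours after dosing and are asked about AEs at every visit, so unknown onset should be rare. The site can also confirm treatment-emergent status, but the SAP offers that only for an unknown date, not for an unknown time.

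**Conclusion.** The concern holds and is minor. On the causality scale the protocol documents, the related-TEAE table and its overview line carry no information beyond the all-TEAE results: 3 of 3 levels are included. The mismatch between the two scales is certain from the text. The duplication assumes that the EDC has no level below Unlikely and that no TEAE lacks a causality rating. If a Not related level exists, what remains is the pooling of events explained by other conditions with events that are not.

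The all-TEAE, intensity and serious-TEAE tables and the AE listings are unaffected by the causality grouping. The onset rules are a secondary issue. They can move a post-dose event into the non-TEAE listing, probably seldom, and the documents give no basis for a count.

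**What to change.** In SAP 3.4.5.1, define the related group as Possible or Probable, adding Related if the EDC carries it, and show Unlikely as its own row. If the broad grouping is intended, say so and still show Unlikely separately. Check the EDC causality list and use one scale across protocol 6.10.1.1, the EDC and the SAP.

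In SAP 3.3.4.1, count an AE as treatment-emergent unless the available date or time information shows onset before dosing. Apply this to unknown times as well as unknown dates, in place of the 12:00 substitution.

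The cost is SAP wording and one check of the EDC list; no new data are needed. There are two downsides. The related-TEAE count falls wherever Unlikely events exist, though their own row keeps them visible. And because AEs are collected from consent, a few undated screening events may be counted as TEAEs.
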